###### 2) When to collect outcome measure data

At each test time point during the period from the start of treatment with Adcetris until the completion of 16 cycles (or upon discontinuation of treatment with Adcetris)

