### b) Infections

It is expected that Adcetris is used in patients who are immunocompromised due to prior treatment or the prior disease or those who are complicated with infection, and the incidence of infections is likely to be high. Therefore, the profile of infections in Japanese patients as an adverse event of particular interest (i.e., the incidence and temporal relationship with the onset of neutropenia/lymphopenia) will be determined.

c) Neutropenia

It is expected that Adcetris is used in patients with decreased neutrophil count due to prior treatment, which may increase the risk of infection and result in a high incidence of infection/severe infection. It is important to control the neutrophil count to allow for continuation of treatment (including dose reduction and restart of treatment after treatment interruption) in terms of the prevention of infection. Therefore, the profile of neutropenia in Japanese patients as an adverse event of particular interest will be determined (i.e., the status of treatment with Adcetris and neutrophil count control will be assessed and information useful for continuation of treatment with Adcetris will be collected).

d) Infusion reactions

Infusion reactions are characteristic of monoclonal antibody preparations, the profile of infusion reactions in Japanese patients as an adverse event of particular interest (including the status of premedication and the percentage of patients using premedication to prevent infusion reactions [use/non-use of premedication to prevent infusion reactions]) will be determined.

e) Pulmonary disorders

The occurrence of pulmonary disorders in Japanese patients receiving monotherapy with Adcetris as an adverse event of particular interest will be determined.

3) When to collect outcome measure data

From the start of treatment with Adcetris until the completion of 16 cycles (or upon discontinuation of treatment with Adcetris)

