1.4 Handling of test data

Test data will be handled according to the criteria shown below. If there are multiple data for the same criterion, the one with the test date being closest to the date of protocol-specified assessment should be used. If there is no difference in the number of days from the date of protocol-specified assessment, the later value should be used.

The number of days after the date of the initial dose of Adcetris is defined as 1 for the date of the initial dose of Adcetris and 0 for the day before the date of the initial dose of Adcetris.

Time point for testing	Date of protocol-specified assessment	Acceptable time window
At the initial dose of Adcetris	Date of the initial dose of Adcetris	-15 days to the date of the initial dose of Adcetris
After 1 cycle	
 If Cycle 2 is initiated: Date of Cycle 2 If Cycle 2 is not initiated: 21 days after the date of the initial dose of Adcetris 	
 If Cycle 2 is initiated: Date of Cycle 2 If Cycle 2 is not initiated: 21 days after the date of the initial dose of Adcetris

Time point for testing	Date of protocol-specified assessment	Acceptable time window
After 2 cycles	
 • If Cycle 3 is initiated: Date of Cycle 3 • If Cycle 3 is not initiated: 21 days after the date of Cycle 2 	
 • If Cycle 3 is initiated: From the day after the date of Cycle 2 to the day of Cycle 3 • If Cycle 3 is not initiated: From the day after the date of Cycle 2 to 21 days after the date of Cycle 2
After 3 cycles	
 • If Cycle 4 is initiated: Date of Cycle 4 • If Cycle 4 is not initiated: 21 days after the date of Cycle 3 	
 • If Cycle 4 is initiated: From the day after the date of Cycle 3 to the day of Cycle 4 • If Cycle 4 is not initiated: From the day after the date of Cycle 3 to 21 days after the date of Cycle 3
After 4 cycles	
 • If Cycle 5 is initiated: Date of Cycle 5 • If Cycle 5 is not initiated: 21 days after the date of Cycle 4 	
 • If Cycle 5 is initiated: From the day after the date of Cycle 4 to the day of Cycle 5 • If Cycle 5 is not initiated: From the day after the date of Cycle 4 to 21 days after the date of Cycle 4

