5.8 Change in test data over time

5.8.1 Change in laboratory test results over time

(1) Analysis sets to be used

Safety analysis set, safety analysis set (Hodgkin's lymphoma), and safety analysis set (anaplastic large-cell lymphoma)

(2) Data to be analyzed

Summary statistics of red blood cell count, hemoglobin level, white blood cell count, neutrophil count, lymphocyte count, platelet count, total bilirubin, AST, ALT, LDH, BUN, and serum creatinine will be calculated at each test time point [at baseline, after 1 cycle, ... and after 15 cycles]. In addition, box plots of hemoglobin level, neutrophil count, lymphocyte count, and platelet count will be generated at each test time point.

(3) Figure/table number

Tables 5.8.1-1 to 5.8.1-3 and Figures 5.8.1-1 to 5.8.1-3

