1.4 Handling of test data

Test data will be handled according to the criteria shown below. If there are multiple data for the same criterion, the one with the test date being closest to the date of protocol-specified assessment should be used. If there is no difference in the number of days from the date of protocol-specified assessment, the later value should be used.

The number of days after the date of the initial dose of Adcetris is defined as 1 for the date of the initial dose of Adcetris and 0 for the day before the date of the initial dose of Adcetris.

Time point for testing	Date of protocol-specified assessment	Acceptable time window
At the initial dose of Adcetris	Date of the initial dose of Adcetris	-15 days to the date of the initial dose of Adcetris
After 1 cycle	
 If Cycle 2 is initiated: Date of Cycle 2 If Cycle 2 is not initiated: 21 days after the date of the initial dose of Adcetris 	
 If Cycle 2 is initiated: Date of Cycle 2 If Cycle 2 is not initiated: 21 days after the date of the initial dose of Adcetris
After 2 cycles	
 If Cycle 3 is initiated: Date of Cycle 3 If Cycle 3 is not initiated: 21 days after the date of Cycle 2 	
 If Cycle 3 is initiated: From the day after the date of Cycle 2 to the day of Cycle 3 If Cycle 3 is not initiated: From the day after the date of Cycle 2 to 21 days after the date of Cycle 2
After 3 cycles	
 If Cycle 4 is initiated: Date of Cycle 4 If Cycle 4 is not initiated: 21 days after the date of Cycle 3 	
 If Cycle 4 is initiated: From the day after the date of Cycle 3 to the day of Cycle 4 If Cycle 4 is not initiated: From the day after the date of Cycle 3 to 21 days after the date of Cycle 3

Time point for testing	Date of protocol-specified assessment	Acceptable time window
After 4 cycles	
 • If Cycle 5 is initiated: Date of Cycle 5 • If Cycle 5 is not initiated: 21 days after the date of Cycle 4 	
 • If Cycle 5 is initiated: From the day after the date of Cycle 4 to the day of Cycle 5 • If Cycle 5 is not initiated: From the day after the date of Cycle 4 to 21 days after the date of Cycle 4

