2.2 Analysis of items of particular interest

2.2.1 Treatment-related infections reported within 7 days after the date of the worst grade of Grade 3 or 4 neutropenia or the date of onset of Grade 3 or 4 decreased neutrophil count considered related to Adcetris

(1) Analysis sets to be used

Patients included in the safety analysis set with confirmed Grade 3 or 4 neutropenia or decreased neutrophil count considered related to Adcetris

(2) Data to be analyzed

The number and percentage of patients experiencing treatment-related infections reported within 7 days after the date of the worst grade of Grade 3 or 4 neutropenia or the date of onset of Grade 3 or 4 decreased neutrophil count considered related to Adcetris will be calculated by infection and PT (for the definition of infection, see Section 1.2). PTs will be presented in ascending order of PT codes.

2.2.2 Treatment-related infections reported within 7 days after the date of the worst grade of Grade 3 or 4 lymphopenia or the date of onset of Grade 3 or 4 decreased lymphocyte count considered related to Adcetris

(1) Analysis sets to be used

Patients included in the safety analysis set with confirmed Grade 3 or 4 lymphopenia or decreased lymphocyte count considered related to Adcetris

(2) Data to be analyzed

The number and percentage of patients experiencing treatment-related infections reported within 7 days after the date of the worst grade of Grade 3 or 4 lymphopenia or the date of onset of Grade 3 or 4 decreased lymphocyte count considered related to Adcetris will be calculated by infection and PT (for the definition of infection, see Section 1.2). PTs will be presented in ascending order of PT codes.

Supplemental Statistical Analysis Plan 2

Additional Analysis on Neutropenia

ADCETRIS IV Infusion – Special Drug Use Surveillance (All-case Surveillance) "Relapsed or Refractory CD30+ Hodgkin's Lymphoma or Anaplastic Large Cell Lymphoma"

PPD

Takeda Pharmaceutical Company Limited

PPD

Initial version: Prepared on November 21, 2017

Table of Contents

1.0	Definition of Analysis sets and Terms and Handling of Test/Measurement Data.....	1
1.1	Analysis sets	1
1.1.1	Safety analysis set.....	1
1.2	Definition.....	1
1.3	Display digits.....	3
1.4	Handling of missing data.....	3
1.5	Others.....	3
2.0	Safety Analysis	4
2.1	Analysis of items of particular interest.....	4
2.1.1	Occurrence of neutropenia considered related to Adcetris by patient demographics and baseline characteristics	4

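### SAP 1.4 keeps one laboratory value per cycle, nearest the next dose, with a one-day window after Cycle 1 and none after Cycle 16, so low counts between doses can be lost or dated late

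*SAP*

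**What the plan says.** I take the SAP version that names MedDRA 19.1 for the final analysis as current. Its section 1.4 and Supplemental SAP 1.4 give the same table.

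- **Selection.** Where a window holds several values, "the one with the test date being closest to the date of protocol-specified assessment should be used".
- **Assessment date.** It is the next dosing date, for example "If Cycle 3 is initiated: Date of Cycle 3". If no further cycle is given, it is 21 days after the last dose.
- **Window.** For cycles 2 to 15 it spans the whole interval between doses, for example "If Cycle 3 is initiated: From the day after the date of Cycle 2 to the day of Cycle 3". For the row after 1 cycle it is one day: the date of Cycle 2, or day 21 after the initial dose. The last row is after 15 cycles.
- **Collection.** Protocol 9.2.4.1 collects laboratory tests "At each test time point during the period from the start of treatment with Adcetris until the completion of 16 cycles".
- **Main use.** SAP 5.8.1 gives summary statistics "at baseline, after 1 cycle, ... and after 15 cycles", with box plots for hemoglobin, neutrophils, lymphocytes and platelets.
- **Infection timing.** Protocol 9.2.5, under infections, sets out to determine "the incidence and temporal relationship with the onset of neutropenia/lymphopenia". Supplemental SAP 2.2.1 counts treatment-related infections within 7 days after either of two dates. One is the worst-grade date of a Grade 3 or 4 neutropenia adverse event. The other is "the date of onset of Grade 3 or 4 decreased neutrophil count considered related to Adcetris". Section 2.2.2 does the same for lymphocytes.

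**The concern.** Every window ends on its own assessment date, so the closest value is always the latest one in the window. In cycles 2 to 15 a low count between doses is dropped whenever a later test exists in the same interval. In cycle 1 it is dropped even if it is the only test. After dose 16 nothing is kept.

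Two outputs are at stake. The 5.8.1 summaries and plots would mostly describe patients about to be dosed again, with no view of how low counts went in between. In Supplemental SAP 2.2, the laboratory route is the only one dated from onset, which is what the protocol's infection aim refers to. If that route uses the windowed values, a count that recovered before the next dose is never seen, and a count still low at the next dose is given too late an onset date.

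**Working it through.** **Inputs.** 16 cycles of 3 weeks (Protocol 7.1); windows (SAP 1.4 and Supplemental SAP 1.4); low counts of neutrophils below 1,000/mm³ and lymphocytes below 500/mm³ (Supplemental SAP 1.2); 7-day infection window (Supplemental SAP 2.2). The plan states no figure for this rule, so there is none to reproduce.

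**Assumptions.** Dosing exactly on schedule, on days 1, 22, ..., 316, with follow-up to day 337. The infection window is read as day 0 to day 7, which is 8 days.

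**1. Days covered.**
- Post-dose days 2 to 337: 336.
- Cycle 1: day 22 only, 1 day.
- Cycles 2 to 15: days 23 to 316, 14 × 21 = 294 days.
- Covered: 1 + 294 = 295. Not covered: 336 − 295 = 41, made up of days 2 to 21 (20 days) and days 317 to 337 (21 days).

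**2. Values kept.** At most 15 post-baseline values per test. Test frequency is not given, so an assumed range, each pattern including a test 21 days after each dose:

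| Tests per cycle | Total over 16 cycles | Kept | Dropped |
|---|---|---|---|
| 3 (weekly) | 48 | 15 | 33 |
| 2 | 32 | 15 | 17 |
| 1 (pre-dose) | 16 | 15 | 1 |

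**3. A missed fall (illustration, second cycle).** Doses on days 22 and 43; neutrophils 600 on day 32 and 2,400 on day 43. Distances to the assessment date are |32 − 43| = 11 and |43 − 43| = 0, so 2,400 is kept and the count below 1,000 disappears. In cycle 1 the same pattern fails for a different reason: a count on day 11 lies outside the one-day window and is never a candidate.

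**4. A late onset (illustration).** Neutrophils 600 on day 32 and 900 on day 43, infection on day 34. Dated from day 32, the infection is 2 days after onset and counts. Dated from day 43, it is 9 days before onset and does not.

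In general, if the retained low value is g days after the first low value, the correct window days retained are max(0, 8 − g), and the wrong days added are min(g, 8):

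| g (days) | Correct days retained, of 8 | Wrong days added |
|---|---|---|
| 1 | 7 | 1 |
| 3 | 5 | 3 |
| 5 | 3 | 5 |
| 7 | 1 | 7 |
| 8 or more | 0 | 8 |

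On schedule, g can reach 20 days within a window of cycles 2 to 15 (day after one dose to the day of the next).

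**5. Does 1.4 feed 2.2?** Supplemental SAP 1.4 says without exception that test data are handled by its table. Section 2.1 there is event-based; only 2.2.1 and 2.2.2 need laboratory counts, so 1.4 has no other visible use. Supplemental SAP 2, which analyses no post-baseline counts, has no test-data section. Against this, 2.2 refers only to section 1.2, and 1.2 defines a low count without any time point. The inference is strong, but the text does not state it.

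**The case against.** The strongest reply is that 2.2.1 and 2.2.2 never cite 1.4. A date of onset can be read as the date of the first recorded count below the cut-off, and the Supplemental SAP also carries over text it does not use, such as percentages for patients excluded from the safety set. This stands as a limit on certainty. It does not remove the problem, because a programmer who follows the text as written would apply 1.4.

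The laboratory-only group may also be small. Section 2.2 requires the low count to be considered related to Adcetris, yet causality is recorded only for adverse events (Protocol 9.2.5 and Table 3). Abnormal laboratory findings can themselves be adverse events (Table 1), and neutropenia is an event of particular interest. This stands, and it shows a second gap: how relatedness applies to a bare count is not stated.

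On 5.8.1, Protocol 10.4.3 promises only baseline and post-baseline summary statistics, which one value per time point satisfies. Per-cycle minima are thus an addition to what was promised. Where sites test only before dosing, cycles 2 to 15 lose nothing, and a mid-cycle value survives there if it is the only or the latest one. Both points stand.

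A reader might infer that the plan misses neutropenia in general. The documents do not support that. Grade 3 or 4 events reported as adverse events enter 2.2 by their worst-grade date whatever the laboratory windows do. SAP 5.9.7 to 5.9.9, SAP 5.11 and Supplemental SAP 2 analyse neutropenia without windowed post-baseline counts.

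**Conclusion.** The point holds in limited form. The selection rule, the one-day window after Cycle 1 and the missing row after Cycle 16 are plain in the text. On schedule, 41 of 336 post-dose days cannot contribute a value, and SAP 5.8.1 shows mostly pre-dose counts.

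The effect on Supplemental SAP 2.2.1 and 2.2.2 is conditional on 1.4 being applied there. It then concerns only low counts identified by laboratory value alone: they can be missed, or their onset dated late enough to lose part or all of the 7-day infection window.

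The share of patients affected cannot be computed, because test frequency, the timing of the lowest counts and the share of low counts not reported as adverse events are not given. For scale only, the 20% frequency of Grade 3 or higher neutropenia in Protocol 3.2 gives 0.20 × 140 = 28 patients. In a denominator of that size, one patient is 1/28 = 3.6 percentage points. That frequency comes from non-Japanese phase 2 studies and does not estimate the laboratory-only group.

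**What to change.** - **Supplemental SAP 2.2.1 and 2.2.2:** state that all recorded counts are used regardless of the 1.4 windows, with onset the first date below the cut-off. State how relatedness to Adcetris is applied to a count not reported as an adverse event.
- **Scope of 1.4:** limit it, in both documents, to by-time-point summaries.
- **After 1 cycle:** let the window run from the day after the initial dose to the date of Cycle 2, or to 21 days after the initial dose if Cycle 2 is not given.
- **After 16 cycles:** add a row in 1.4 and a time point in 5.8.1, running from the day after Cycle 16 to 21 days after it, or to the next dose if one is given.
- **SAP 5.8.1:** keep the existing summaries and add the lowest value per cycle for neutrophils, lymphocytes, platelets and hemoglobin.

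With the two windows completed, all 336 on-schedule post-dose days are covered. With all counts used in 2.2, all 8 days after the first recorded low count are kept. The cost is SAP wording and some programming on data already collected. The drawback is that a minimum depends on how often a site tests, so the number of tests per cycle should be shown beside it.

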1.5 Handling of missing data

- As a general rule, missing data will not be imputed.
- In the analysis of the frequency qualitative variables, missing data will be handles as “unknown.”

1.6 Others

- In the analysis for the preparation of documents for the Final Survey Report, MedDRA version 19.1 will be used for adverse events, concurrent illness, and past history.
- If a patient has multiple data for a single laboratory test and date of testing, the mean value will be calculated for the analysis of laboratory test results.

2.0 Safety Analysis

2.1 Seriousness, CTCAE Grade (the worst one), time of onset, time to the worst grade, and occurrences of adverse drug reactions/infections by outcome

(1) Analysis sets to be used

Safety analysis set, safety analysis set (Hodgkin's lymphoma), and safety analysis set (anaplastic large-cell lymphoma)

(2) Data to be analyzed

For each data item, patients will be stratified into the following categories, and the type of adverse events will be analyzed:

Data item	Category
Seriousness	Serious or non-serious
CTCAE Grade (the worst one)	Grade 1, Grade 2, Grade 3, Grade 4, Grade 5, or unknown
Time of onset	1 to 7 days, 8 to 14 days, 15 to 21 days, 22 to 84 days, 85 to 168 days, 169 to 252 days, 253 to 336 days, ≥ 337 days, or unknown
	1 to 21 days, 22 to 42 days, 43 to 63 days, (segmented similarly using a 21-day time window thereafter), 316 to 336 days, ≥ 337 days, or unknown
Time to the worst grade	1 to 7 days, 8 to 14 days, 15 to 21 days, 22 to 84 days, 85 to 168 days, 169 to 252 days, 253 to 336 days, ≥ 337 days, or unknown
	1 to 21 days, 22 to 42 days, 43 to 63 days, (segmented similarly using a 21-day time window thereafter), 316 to 336 days, ≥ 337 days, or unknown
Outcome	Recovered/resolved, recovering/resolving, not recovered/not resolved, recovered/resolved with sequelae, died/fatal, unknown, or not provided

The type of adverse events will be analyzed as follows:

Data item	Data to be analyzed
Number of patients	Number of patients with adverse events by SOC/PT
Number of adverse events, etc.	Number of adverse events observed by SOC/PT If the same patient has multiple occurrences of the same adverse event (PT), all these occurrences will be counted (i.e., the overlap should be reflected).
Seriousness, time of onset, and outcome	The number of adverse events will be calculated by SOC and PT. SOCs will be presented in the internationally agreed order, and PTs will be presented in ascending order of HLG and PT codes if their SOCs are "Investigations," and in ascending order of PT code otherwise. If the same patient has multiple occurrences of the same adverse

	
event (PT), the total number of occurrences will be calculated per category (for example, if the same patient has one episode of serious diarrhea and one episode of non-serious diarrhea, these events will be counted once for each category). If the same patient has multiple occurrences of the same adverse event classified into the same category, all these occurrences will be counted (i.e., the overlap should be reflected).

CTCAE Grade (the worst one) and time to the worst grade
	
The number of adverse events will be calculated by SOC and PT. The CTCAE grade is higher in the order of Grade 5, 4, 3, 2, 1, and unknown. The event with the highest CTCAE grade (the worst one) and the shortest time to the worst grade will be counted once.

2.2 Analysis of items of particular interest

2.2.1 Treatment-related infections reported within 7 days after the date of the worst grade of Grade 3 or 4 neutropenia or the date of onset of Grade 3 or 4 decreased neutrophil count considered related to Adcetris

(1) Analysis sets to be used

Patients included in the safety analysis set with confirmed Grade 3 or 4 neutropenia or decreased neutrophil count considered related to Adcetris

(2) Data to be analyzed

The number and percentage of patients experiencing treatment-related infections reported within 7 days after the date of the worst grade of Grade 3 or 4 neutropenia or the date of onset of Grade 3 or 4 decreased neutrophil count considered related to Adcetris will be calculated by infection and PT (for the definition of infection, see Section 1.2). PTs will be presented in ascending order of PT codes.

2.2.2 Treatment-related infections reported within 7 days after the date of the worst grade of Grade 3 or 4 lymphopenia or the date of onset of Grade 3 or 4 decreased lymphocyte count considered related to Adcetris

(1) Analysis sets to be used

Patients included in the safety analysis set with confirmed Grade 3 or 4 lymphopenia or decreased lymphocyte count considered related to Adcetris

(2) Data to be analyzed

The number and percentage of patients experiencing treatment-related infections reported within 7 days after the date of the worst grade of Grade 3 or 4 lymphopenia or the date of onset of Grade 3 or 4 decreased lymphocyte count considered related to Adcetris will be calculated by infection and PT (for the definition of infection, see Section 1.2). PTs will be presented in ascending order of PT codes.

Supplemental Statistical Analysis Plan 2

Additional Analysis on Neutropenia

ADCETRIS IV Infusion – Special Drug Use Surveillance (All-case Surveillance) "Relapsed or Refractory CD30+ Hodgkin's Lymphoma or Anaplastic Large Cell Lymphoma"

PPD

Takeda Pharmaceutical Company Limited

PPD

Initial version: Prepared on November 21, 2017

Table of Contents

1.0	Definition of Analysis sets and Terms and Handling of Test/Measurement Data.....	1
1.1	Analysis sets	1
1.1.1	Safety analysis set.....	1
1.2	Definition.....	1
1.3	Display digits.....	3
1.4	Handling of missing data.....	3
1.5	Others.....	3
2.0	Safety Analysis	4
2.1	Analysis of items of particular interest.....	4
2.1.1	Occurrence of neutropenia considered related to Adcetris by patient demographics and baseline characteristics	4

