#### 9.2.5 Adverse events

##### 1) Outcome measures

Presence/absence of adverse events (see Table 1), adverse event terms, date of onset, CTCAE grade (the worst one), seriousness and its reason (see Table 2), (presence/absence and detail of) action taken to Adcetris, (presence/absence and detail of) intervention for adverse events, date of outcome, outcome, causal relationship with Adcetris\* (see Table 3), and changes in laboratory test values associated with adverse events over time

If the outcome is “not recovered/not resolved” or “unknown,” and the causal relationship with Adcetris is considered unevaluable, the event should be followed wherever possible.

\* If the event is considered not related to Adcetris, its rationale should be collected. If the causal relationship with Adcetris is considered unevaluable, its reason should be collected.

Note) Points to consider regarding adverse events

Worsening of the primary disease should not be regarded as an adverse event. However, abnormal worsening of the primary disease (e.g., worsening beyond the expected natural course of the disease) should be regarded as an adverse event.

Disease progression should be regarded as worsening of the primary disease rather than an adverse event. However, clinical or laboratory progression of an existing cancer (including new metastasis) that meets any of the criteria for the seriousness of adverse events (see Table 2) should be considered a serious adverse event.

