Time of onset	
Is calculated using the following formula: date of onset of adverse events (or adverse drug reactions, etc.) – date of the initial dose of Adcetris + 1.
 
If the day, month, and year of onset of adverse events (or adverse drug reactions, etc.) are unknown, the time of onset should be handled as missing, and the category for the time of onset should be “unknown.”

Time to the worst grade	
Is calculated using the following formula: date of the worst CTCAE grade – date of the initial dose of Adcetris + 1.
 
If the day, month, and year of the worst CTCAE grade are unknown, the date of the worst CTCAE grade should be handled as missing, and the category for the date of the worst CTCAE grade should be “unknown.”

Infection	A concurrent illness or adverse event that falls under the category of MedDRA SOC Code 10021881 (Infections and infestations)
Grade 3 or 4 decreased neutrophil count	Neutrophil count <1,000/mm ³
Grade 3 or 4 decreased lymphocyte count	Lymphocyte count < 500/mm ³
Neutropenia	An adverse event equivalent to MedDRA PT Codes 10029366 (Neutrophil count decreased) and 10029354 (Neutropenia).
Lymphopenia	An adverse event equivalent to MedDRA PT Codes 10025256 (Lymphocyte count decreased) and 10025327 (Lymphopenia).

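### Supplemental SAP 2.2.1 and 2.2.2 start the 7-day infection window from two unreconciled dates, worst grade for adverse events and onset for laboratory counts, while the protocol asks about onset

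*SAP*

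**What the plan says.** Protocol 9.2.5, under infections as an event of particular interest, says that the surveillance will determine "the incidence and temporal relationship with the onset of neutropenia/lymphopenia". It sets no grade limit and no window length.

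The Supplemental SAP prepared in September 2017 addresses this in 2.2.1 and 2.2.2. For neutropenia it counts treatment-related "infections reported within 7 days after the date of the worst grade of Grade 3 or 4 neutropenia", and the sentence continues "or the date of onset of Grade 3 or 4 decreased neutrophil count considered related to Adcetris". For lymphopenia the wording is parallel: "infections reported within 7 days after the date of the worst grade of Grade 3 or 4 lymphopenia", then "or the date of onset of Grade 3 or 4 decreased lymphocyte count considered related to Adcetris". The neutropenia analysis set is patients "with confirmed Grade 3 or 4 neutropenia or decreased neutrophil count considered related to Adcetris".

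Section 1.2 of the supplement defines the Grade 3 or 4 counts by laboratory value: neutrophils below 1,000/mm³ and lymphocytes below 500/mm³. Neutropenia and lymphopenia themselves are defined as coded adverse events, and these include the terms for a decreased count. The adverse-event items in Protocol 9.2.5 run "adverse event terms, date of onset, CTCAE grade (the worst one), seriousness and its reason" and later include the date of outcome. A date of worst grade is not named there.

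**The concern.** The protocol's question is about onset. In the adverse-event arm the clock starts only at the worst grade, so that arm cannot count an infection that begins while neutrophils are falling. The laboratory arm does start at onset. The same fall in neutrophils can therefore be timed from either date, depending on whether it reached the database as a coded event or as a count, and the results are pooled in one percentage.

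This matters because 2.2 is the only planned analysis that relates the timing of infection to cytopenia. Main SAP 5.9.5 and 5.9.6 tabulate infections by prophylaxis and by prior transplantation. Supplement 2 analyses neutropenia without linking it to infection. If 2.2 does not answer the onset question, nothing else in the plan does.

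**Working it through.** The plan gives no figure on this point to reproduce. The check is to apply the rule as written, day by day.

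**Inputs.** The two anchors and the 7-day length come from Supplemental SAP 2.2, the count thresholds from 1.2, the selection of test values from 1.4, and the no-imputation rule from 1.5.

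**Assumptions.** Days 0 to 7 after an anchor are counted inclusively. An infection is dated by its start. The gaps and episode lengths below are illustrative and do not come from the documents.

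**Rule.** Let L be the day of the first Grade 3 or 4 count, W the day of worst grade and I the infection day. The infection is counted if 0 ≤ I − W ≤ 7, or, where a count was captured, if 0 ≤ I − L ≤ 7.

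**Step 1: infections before the worst date.** Set L = 0 and W = G, which leaves G possible infection days before the worst date. The adverse-event arm alone counts none, because I < W. With a captured count, the number counted is the smaller of G and 8.

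| Gap G (days) | Counted, count captured | Counted, no count captured |
|---|---|---|
| 3 | 3 of 3 | 0 of 3 |
| 5 | 5 of 5 | 0 of 5 |
| 8 | 8 of 8 | 0 of 8 |
| 10 | 8 of 10 | 0 of 10 |
| 14 | 8 of 14 | 0 of 14 |
| 21 | 8 of 21 | 0 of 21 |

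**Step 2: infections before the count reaches Grade 3.** Take adverse-event onset on day 0, L = 5 and W = 9. Days 5 to 16 are counted. Days 0 to 4 are not, although they follow the onset of the event.

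**Step 3: share of an episode.** Take an episode on days 1 to 14, worst grade on day 5, and constant infection hazard.
- No count captured: the window is days 5 to 12. Days 1–4 and 13–14 are missed, 4 + 2 = 6 of 14 (43%).
- Count captured on day 1: the windows are days 1–8 and 5–12, together days 1 to 12. Days 13–14 are missed, 2 of 14 (14%).

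The difference, 4 of 14 days, is due to the anchor. The remaining 2 days are due to the 7-day length and are missed either way.

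**Step 4: will the count be captured?** Section 1.4 of the supplement keeps one value per cycle, the one closest to the next dosing date. For Cycle 1, when Cycle 2 is given, the only acceptable date is the day of Cycle 2 itself. Suppose a count falls below 1,000/mm³ on day 10 and has recovered when Cycle 2 is given on day 22. Under 1.4 the day-10 value is ineligible and no onset date arises. In later cycles a mid-cycle value is eligible but gives way to one nearer the next dose, so onset can be lost or dated late. Section 2.2 does not say whether 1.4 applies. However, 2.1 concerns adverse reactions, and no other analysis in that supplement uses test counts.

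**The case against.** The strongest reply is that the sentence already contains an onset arm. The protocol collects neutrophil and lymphocyte counts at each test time point, and also laboratory changes associated with adverse events. A Grade 3 or 4 event will therefore often have a recorded count below the threshold, and Step 1 shows that such a count brings in earlier infections up to 7 days after it. The protocol also fixes no window length, so a short window is a legitimate choice. Opening at adverse-event onset would admit Grade 1 and 2 days into a Grade 3 or 4 analysis.

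All of this stands, and it rules out several stronger readings:

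- *No infection before the worst date is counted.* This is true of the adverse-event arm alone, not of the rule as written.
- *Close to half of infections during cytopenia are lost.* The 6 of 14 days holds only for the assumed episode and only when no count is captured.
- *Infections late in a long episode show that the anchor is wrong.* They reflect the window length; a 7-day window from onset would miss them too.
- *The association between infection and cytopenia is understated.* Section 2.2 is a descriptive percentage among patients with cytopenia. It has no comparator and estimates no association. The window can also run past recovery, so the net direction of any error in the percentage is not established.
- *The date of worst grade is not collected.* The supplement has a rule for when that date is unknown, which suggests that it is recorded, and the case report form is not among the documents. What remains is that an event with a known onset but an unknown worst date yields no window from the adverse-event arm, because dates are not imputed.

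The reply does not dispose of 1.4. If that rule governs 2.2, the onset arm fails for many mid-cycle counts. Nor does it explain why the two sources use different dates or which prevails.

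**Conclusion.** The point holds as a mismatch of anchors with a limited gap. The adverse-event arm departs from the protocol's onset question without a stated reason, the laboratory arm follows it only for Grade 3 or 4 counts, and the two are not reconciled. Infections between cytopenia onset and the worst date are missed in the three situations shown: no qualifying count captured, infection before the first such count, or infection more than 7 days after it.

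The number of infections affected cannot be computed, because the documents give neither episode lengths nor the gap between onset and worst grade. The figures of 2 and 6 of 14 days are illustrations that rest on constant hazard, inclusive counting of days 0 to 7, and the assumed episode. Which figure is closer to practice depends mainly on whether 1.4 restricts the counts used in 2.2. The plan leaves that open.

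**What to change.** In 2.2.1 and 2.2.2:

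1. Add a row that opens the window at onset for both sources: the adverse-event date of onset, or the first recorded count below the threshold.
2. State that all recorded counts, not only those selected under 1.4, define laboratory onset, and that the earlier date applies when both exist.
3. Keep the worst-date version as a separate, labelled row.

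The onset row is there to answer the protocol's question on one anchor, not to cover more days. In the 14-day illustration with onset on day 1 it would cover days 1 to 8.

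A row running from onset to recovery is optional as a sensitivity analysis. It would give windows of unequal length and needs a rule for events recorded as not recovered.

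The cost is supplemental wording and two re-run tables; adverse-event onset dates and counts are already collected. The downside is that adverse-event onset can precede Grade 3, so some window days will cover a lower grade. A footnote should say so.
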